## 9.5.2.2 Description of Procedures/Assessments Schedule

### 9.5.2.2.1 Visit 1 (Screening, -3 weeks ~ -1 day)

All procedures will be conducted after obtaining informed consent from subjects who want to participate in this clinical trial. After obtaining informed consent, the following procedures will be performed to establish eligibility for the trial:

- Demography
- Height
- Weight
- Medical history
- Prior and concomitant medications
- Concomitant therapies
- Clinical laboratory tests
- 12-lead ECG: if deemed necessary by an investigator based on subject's symptoms
- Vital signs
- Urine pregnancy test
- Physical examinations
- AE assessment
- Subjects and/or their caregivers receive a subject diary and investigator will train them how to complete a diary.
- Conduct the MMSE among the efficacy assessments.

During Screening Period, if subjects have previously taken medication such as COMT inhibitor and/or MAO-B inhibitor, they have to undergo an appropriate wash-out period for each medication.

Subjects who meet the eligibility criteria of the study will be instructed to complete the diary for 3 consecutive days prior to Visit 2 (Baseline).

**9.5.2.2.2 Visit 2 (Baseline, 0 week)**

At Visit 2 (Baseline), the following procedures will be performed:

- Reconfirmation of eligibility assessment
- Weight: if deemed necessary by an investigator
- Concomitant medications
- Concomitant therapies
- Vital signs
- Physical examinations
- Study drug dispensation
- AE assessment
- Efficacy assessments including PDQ-39, MDS-UPDRS Part 3 and Part 4, and KPPS, are performed. The completed subject diary will be reviewed by an investigator together with a subject.

If MMSE was not conducted at Visit 1 (Screening), it can be performed at Visit 2 (Baseline). If MMSE is conducted at either Visit 1 (Screening) or Visit 2 (Baseline), the subject will be considered to have completed the MMSE.

**9.5.2.2.3 Visit 3 (8 weeks, -4/+2 weeks)**

At Visit 3, the following procedures will be performed:

- Weight: if deemed necessary by an investigator
- Concomitant medications
- Concomitant therapies
- Clinical laboratory tests
- 12-lead ECG: if deemed necessary by an investigator based on subject's symptoms
- Vital signs
- Physical examinations

- Study drug dispensation
- Unused study drug return
- Study drug compliance check
- AE assessment

#### **9.5.2.2.4 Visit 4 (EOT; 18 weeks, +/-2 weeks)**

At Visit 4 (EOT), the following procedures will be performed:

- Weight
- Concomitant medications
- Concomitant therapies
- Clinical laboratory tests
- 12-lead ECG: if deemed necessary by an investigator based on subject's symptoms
- Vital signs
- Urine pregnancy test
- Physical examinations
- Dispensation of study drug(only if tapering period is conducted)
- Return of unused study drug
- Check compliance of the study drug
- AE assessment
- Efficacy assessments including PDQ-39, MDS-UPDRS Part 3 and Part 4, KPPS, and MMSE are performed. The completed subject diary will be reviewed by an investigator with a subject.

Of the subjects who have completed Visit 4(EOT), those who require tapering will enter a Taper Period for 1 week. After the completion of the Taper Period, subjects will return to the site for Visit 5.

The Taper Period may be omitted if the subject's daily dose of study drug at the end of treatment is 50mg, if subjects will continue to take the study drug after the completion of the trial, or if it is considered not required by an investigator. For the subjects who do not require

the Taper Period, their participation in the study will be completed after Visit 4, the End of Treatment Visit.

If a subject is withdrawn from the study before Visit 4 (EOT), Premature Discontinuation Visit should be completed as soon as practicable after discontinuing study drug (preferably within 7 days). Following the completion of Premature Discontinuation Visit, subjects who require taper will undergo a Taper Period for 1 week. Then the subjects will return to the site for Visit 5. For the subjects who do not require a Taper Period, Premature Discontinuation Visit would be their last visit in the study.

#### **9.5.2.2.5 Visit 5 (19 weeks, +1 week)**

After the completion of Taper Period, subjects will undergo the following examinations at Visit 5:

- Weight: if deemed necessary by an investigator
- Concomitant medications
- Concomitant therapies
- Clinical laboratory tests: if deemed necessary by an investigator based on subject's symptoms
- 12-lead ECG: if deemed necessary by an investigator based on subject's symptoms
- Vital signs
- Physical examinations
- Unused study drug return
- Study drug compliance check
- AE assessment

#### **9.5.2.2.6 Unscheduled Visit**

Subjects can additionally visit separately from a scheduled visit if medical treatment is needed in case of abnormal test result or AE occurs, or follow-up is needed after the occurrence of AE.

Subjects may conduct an unscheduled visit after Visit 2 (Baseline) if examination is required prior to increasing the dose of study drug (from 50 mg/day to 100 mg/day).

If the dose reduction (from 100mg/day to 50mg/day) is required due to events such as AE, the dose may be reduced back to 50mg/day at the discretion of an investigator through

unscheduled site visit or phone visit. In the case of a phone visit, the information such as date of study drug dose change (start date of dose reduction) and relevant Adverse Events shall be collected.

If subjects need to increase the dose back to 100mg/day after the reduction to 50mg/day, they may conduct an unscheduled site visit and the dose may be increased back to 100mg/day at the discretion of an investigator.

### 9.5.3 Appropriateness of Measurements

All clinical assessments performed in this study are standard measurements commonly used in studies of Parkinson's Disease.

### 9.5.4 Reporting of Serious Adverse Events and Events Associated with Special Situations

#### 9.5.4.1 Reporting of Serious Adverse Events

**All SERIOUS ADVERSE EVENTS, regardless of their relationship to study drug, must be reported on a completed SAE form as soon as possible but no later than 24 hours from the date an investigator becomes aware of the event.**

All SAEs must be followed to resolution or, if resolution is unlikely, to stabilization. Any SAE judged by the investigators to be related to the study drug or any protocol-required procedure should be reported to the sponsor regardless of the length of time that has passed since study completion.

The detailed contact information for reporting of SAEs is provided in the Investigator Study File.

**For urgent safety issues**, please ensure all appropriate medical care is administered to the subject and contact the appropriate study team member listed in the Investigator Study File.

It is very important that the SAE report form be filled out as completely as possible at the time of the initial report. This includes an investigator's assessment of causality.

Any relevant follow-up information received on SAEs should be forwarded within 24 hours of its receipt. If the relevant follow-up information changes the investigator's assessment of causality, this should also be noted on the follow-up SAE form.

Preliminary SAE reports should be followed as soon as possible by detailed descriptions, including copies of site case reports, autopsy reports, and other documents requested by the sponsor.

#### **9.5.4.2 Reporting of Events Associated with Special Situations**

The following special situations must be collected and reported in the same manner as SAEs regardless of occurrence of adverse events.

- Pregnancy: paternal/maternal exposure
- Breastfeeding
- Lack of therapeutic efficacy
- Drug interactions
- Suspected transmission of infectious agents
- Overdose, abuse, off-label use, misuse, medication error, and occupational exposure
- Suspected or confirmed falsified medicinal product

##### **9.5.4.2.1 Reporting of Pregnancy and Exposure to Study Drug Through Breastfeeding**

Any pregnancy in a female subject in which the estimated date of conception is either before the last visit or within 28 days from the last day of administration of the study drug, or any exposure to study drug through breastfeeding during study treatment or within 28 days from the last day of administration of the study drug, must be reported. If an adverse outcome of a pregnancy is suspected to be related to study drug exposure, this should be reported regardless of the length of time that has passed since the exposure to study treatment.

A congenital anomaly, death during perinatal period, a spontaneous abortion, or an induced abortion done due to safety concerns for either mother or fetus are considered to be an SAE and should be reported in the same time frame and in the same format as all other SAEs (refer to Section 9.5.4.1).

Pregnancies or exposure to the study drug through breastfeeding must be reported as soon as possible but no later than 24 hours from the date an investigator becomes aware of the pregnancy. The contact information for the reporting of pregnancies and exposure to the study drug through breastfeeding is provided in the Investigator Study File. The Pregnancy Report Form must be used for reporting. All pregnancies must be followed to outcome. The outcome of the pregnancy must be reported as soon as possible but no later than 24 hours from the date the investigator becomes aware of the outcome.

A subject who becomes pregnant must be withdrawn from the study. A subject who becomes pregnant may remain in the study if an investigator judges that the potential benefit to the subject outweighs any potential risk to the subject or the fetus, and the subject gives informed consent for further participation.

### 9.5.4.2.2 Reporting of Lack of Efficacy

"Efficacy" is defined as:

- The ability of an intervention to produce desired beneficial effect in expert hands and under ideal circumstances
- In pharmacology, the ability of a drug, biologic, or device to produce desired therapeutic effect independent of potency (amount of the product needed for desired effect).

"Effect" is defined as the result produced by an action. Lack of efficacy/effect is, therefore evidence of less than the expected effect of a product. There might be subpopulations that have a higher risk for lack of efficacy/effect; in order to identify such cases, one needs to consider the types of events that may be reported in such situations for the specific product and indication.

All AEs associated with lack of efficacy should be collected on the Adverse Event CRF and reported in an expedited manner using the SAE form regardless of seriousness.

### 9.5.4.2.3 Reporting of Adverse Events Associated with Study Drug Overdose, Misuse, Abuse, or Medication Error

Adverse events associated with study drug overdose, misuse, abuse, and medication error refer to AEs associated with uses of the study drug outside of that specified by the protocol. Overdose, misuse, abuse, and medication error are defined as follows:

Overdose	Accidental or intentional use of the study drug in an amount higher than the protocol-defined dose
Misuse	Intentional and inappropriate use of study drug not in accordance with the protocol. Intentional and inappropriate use of study drug not in accordance with the prescribed or authorized dose, route of administration, or indication(s) or use of prescription-only study drug without a prescription
Abuse	Sporadic or persistent intentional excessive use of study drug accompanied by harmful physical or psychological effects
Medication error	Any unintentional event that causes or leads to inappropriate study drug use or subject harm while the study drug is in the control of site personnel or the subject.

All AEs associated with overdose, misuse, abuse, or medication error should be captured on the Adverse Event CRF and also reported using the procedures detailed in Reporting of Serious Adverse Events (Section 9.5.4.1) even if the AEs do not meet serious criteria. Abuse and Intentional Overdose, even if asymptomatic, are always to be captured as an AE. If the AE associated with an overdose, misuse, abuse, or medication error does not meet serious criteria,

it must still be reported using the SAE form and in an expedited manner but should be noted as nonserious on the SAE form and the Adverse Event CRF.

#### **9.5.4.3 Expedited Reporting**

The sponsor must inform the investigators and regulatory authorities of reportable events, in compliance with applicable regulatory requirements, on an expedited basis (i.e., within specific time frames). For this reason, it is imperative that sites provide complete SAE information in the manner described above.

#### **9.5.4.4 Regulatory Reporting of Adverse Events**

AEs will be reported by the sponsor or a third party acting on behalf of the sponsor to regulatory authorities in compliance with local law and established guidance. The format of these reports will be dictated by the local requirements.

#### **9.5.5 Completion/Discontinuation of Subjects**

In this study, subjects are assumed to have completed the clinical trial upon their completion of Visit 4 (EOT).

A subject may elect to discontinue the study at any time for any reason. All subjects who discontinue the study are to complete the study's early discontinuation procedures indicated in Table 3.

An investigator will promptly explain to the subject involved that the study will be discontinued for that subject and provide appropriate medical treatment and other necessary measures for the subject. A subject who has ceased to return for visits will be followed up by mail, phone, or other means to gather information such as the reason for failure to return, the status of treatment compliance, the presence or absence of AEs, and clinical courses of signs and symptoms.

Subjects who discontinue early from the study will be discontinued for the following reasons: AE, lost to follow-up, withdrawal of consent by subject, lack of efficacy, noncompliance with study procedure, impossibility to increase study drug dose, pregnancy, study terminated by sponsor, or other.

A subject removed from the study for any reason may not be replaced.

### **9.6 Data Quality Assurance**

This study will be organized, performed, and reported in compliance with the protocol, SOPs, working practice documents, and applicable regulations and guidelines. Site audits may be made periodically by the sponsor's or the CRO's qualified compliance auditing team, which is an independent function from the study team responsible for conduct of the study.

### **9.6.1 Data Collection**

Data required by the protocol will be collected on the CRFs and entered into a validated data management system that is compliant with all regulatory requirements. As defined by ICH guidelines, the CRF is a printed, optical, or electronic document designed to record all of the protocol-required information to be reported to the sponsor on each study subject.

Data collection on the CRF must follow the instructions described in the CRF Completion Guidelines. The investigators have ultimate responsibility for the collection and reporting of all clinical data entered on the CRF.

The investigators must sign the completed CRF to attest to its accuracy, authenticity, and completeness.

Completed, original CRFs are the sole property of Eisai Korea Inc. and should not be made available in any form to third parties without written permission from Eisai Korea Inc., except for authorized representatives of Eisai Korea Inc. or appropriate regulatory authorities.

### **9.6.2 Clinical Data Management**

All software applications used in the collection of data will be properly validated following standard computer system validation that is compliant with all regulatory requirements. All data, both CRF and external data (e.g., laboratory data), will be entered into a clinical system.

## **9.7 Statistical Methods**

All statistical analyses will be performed by the sponsor or designee after the study is completed and the database is locked and released. Statistical analyses will be performed using SAS software or other validated statistical software as required. Details of the statistical analyses will be included in a separate statistical analysis plan (SAP).

### **9.7.1 Statistical and Analytical Plans**

The statistical analyses of this study data are described in this section. Further details of the analytical plan will be provided in the SAP, which will be finalized before database lock.

The descriptive statistics for continuous variables are the numbers of subjects, mean, standard deviation, median, minimum, maximum, and for categorical variables are the numbers of subjects and percentage. The statistical testing for efficacy endpoints is conducted using the two-sided test at a 2.5% significance level.

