#### **Study Endpoints**

##### **Co-Primary Endpoints**

- Change at the 18th week from baseline in daily "off" time
- Change at the 18th week from baseline in PDQ-39 score

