### **Sample Size Rationale**

The sample size was calculated assuming the efficacy of this study at 18 weeks is comparable to the efficacy of phase 3 clinical study at 24 weeks. The sample size is calculated using each 2 primary endpoints, and a larger sample size is selected conservatively. The sample size for each evaluation variable is as follows:

- **Endpoint 1: Paired t-test for “off” time**  
Based on the above assumptions, to calculate the number of subjects for the comparison of the “off” time mean change after 24 weeks compared to baseline, sample size was calculated assuming average change (-1.56) and standard deviation (2.35).  
The results were performed through PASS (version 2020), the sample sizes of 31 achieve 90% power and the significance level (alpha) is 0.025.
- **Endpoint 2: Paired t-test for PDQ-39 score**  
Based on the above assumptions, to calculate the number of subjects for the comparison of the PDQ-39 score mean change after 24 weeks compared to baseline, sample size was calculated assuming average change (-3.17) and standard deviation (10.86).  
The results were performed through PASS (version 2020), the sample sizes of 149 achieve 90% power and the significance level (alpha) is 0.025.

According to the above two endpoints, the sample sizes are 31, 149 at each assumption. The sample size of endpoint 2 is larger than endpoint 1. Therefore, the final sample size obtained considering the drop-out rate of 25% during the study period is 199.

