## 9.2 Discussion of Study Design

This study is a multi-center, open-label, single-arm, interventional study to evaluate the efficacy and safety of the study drug as add-on therapy to levodopa in subjects with Parkinson's Disease according to standard clinical practice. The study drug has dopaminergic and non-dopaminergic pathways so it improves motor symptoms as well as non-motor symptoms. For this reason, this study will evaluate the "off" time and PDQ-39 as co-primary endpoints.

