## 9.7.2 Determination of Sample Size

The sample size is calculated under assumption the efficacy of this study at 18 weeks is comparable to the efficacy of phase 3 clinical study at 24 weeks.

The sample size is calculated using each 2 primary endpoints, and a larger sample size is selected conservatively. The sample size for each evaluation variable is as follows.

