#### 1) Endpoint 1: Paired t-test for “off” time

Based on the above assumptions, to calculate the number of subjects for the comparison of the “off” time mean change 24 weeks after Baseline, the sample size was calculated assuming average change (-1.56) and standard deviation (2.35).

The results were performed through PASS (version 2020), the sample sizes of 31 achieve 90% power and the significance level (alpha) is 0.025.

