#### 2) Endpoint 2: Paired t-test for PDQ-39 score

Based on the above assumptions, to calculate the number of subjects for the comparison of the PDQ-39 score mean change 24 weeks after Baseline, the sample size was calculated assuming average change (-3.17) and standard deviation (10.86).

The results were performed through PASS (version 2020), the sample sizes of 149 achieve 90% power, and the significance level (alpha) is 0.025.

According to the above two endpoints, the sample sizes are 31, 149 at each assumption. The sample size of endpoint 2 is larger than endpoint 1. Therefore, the final sample size obtained, considering the drop-out rate of 25% during the study period is 199.

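### Do the two primary endpoints need a written success rule, and Holm in place of two fixed 2.5% tests?

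*Combined protocol and SAP*

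**What the plan says.** The synopsis lists change in daily off time and change in PDQ-39 under the heading "Co-Primary Endpoints". Section 9.2 repeats the label ("time and PDQ-39 as co-primary endpoints") and ties the pairing to the drug's expected effect on both motor and non-motor symptoms. Section 9.7.1 sets the level: "The statistical testing for efficacy endpoints is conducted using the two-sided test at a 2.5% significance level". Section 9.7.1.7.1 gives each primary endpoint a paired t-test on the week-18 change, and Section 9.7.1.7.2 gives the same test to five secondary measures.

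Section 9.7.2 sizes the two endpoints separately. For off time, "the sample sizes of 31 achieve 90% power and the significance level (alpha) is 0.025"; for PDQ-39, "the sample sizes of 149 achieve 90% power, and the significance level (alpha) is 0.025". The larger figure is carried forward and inflated for 25% dropout to 199.

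The text supplied names no multiplicity procedure, states no overall alpha, and does not say whether both endpoints must be significant. It does say where more will appear: "Further details of the analytical plan will be provided in the SAP, which will be finalized before database lock". That separate SAP is not in the text supplied.

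**The concern.** The two cues point in different directions. Co-primary usually means that both endpoints must succeed, and then no split of alpha is needed. A level of 2.5% on each of two endpoints looks like a Bonferroni split of 5%, which serves a claim on either one. If off time is significant and PDQ-39 is not, the protocol text alone does not say what the trial has shown.

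That outcome is the likeliest split. Off time needs 31 subjects and PDQ-39 needs 149, so at the planned size off time is almost certain to reach significance and PDQ-39 decides the rest. The sizing also assumes that "the efficacy of this study at 18 weeks is comparable to the efficacy of phase 3 clinical study at 24 weeks". If the PDQ-39 effect is smaller at 18 weeks, a split result becomes more common. On the either-endpoint reading, Holm would spend the same 5% and never reject less than the fixed tests do, so the fixed split seems to give away power on the endpoint that sets the sample size.

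**Working it through.** **Inputs.** From Section 9.7.2: off time mean change -1.56, SD 2.35; PDQ-39 mean change -3.17, SD 10.86; alpha 0.025; power 90%; dropout 25%. From Section 9.7.1: the tests are two-sided. Assumed for this check: overall alpha 5% (2 × 2.5%) on the either-endpoint reading, and the correlations between endpoints given below.

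**1. The plan's own figures.** Power of a paired t-test comes from the noncentral t distribution with n - 1 degrees of freedom and noncentrality (|mean|/SD) × √n.
- Off time: 1.56/2.35 = 0.664. At n = 31 and two-sided 0.025, power is 90.3% (n = 30 gives 89.1%).
- PDQ-39: 3.17/10.86 = 0.292. At n = 149 and two-sided 0.025, power is 90.2%.
- Enrolment: 149/0.75 = 198.7, rounded up to 199.

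All three reproduce. Two-sided 0.05 would have given 26 and 126, so sizing and analysis use the same level.

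**2. Error control as written.**
- Both must succeed: the worst case is one endpoint certain to pass and the other null, so false success is at most 2.5%. Simulated power to win on both at n = 149 is 90.1% to 90.2% at correlations 0, 0.3 and 0.6.
- Either suffices: the bound is 0.025 + 0.025 = 5%; with independent endpoints it is 1 - 0.975² = 4.94%.

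**3. What Holm would add, on the either-endpoint reading only.** Holm tests the smaller p-value at 2.5% and, if that is significant, the other at 5%. Off-time power at n = 149 exceeds 99.9% even at 0.7 times the planned effect, so PDQ-39 would in practice be tested at 5%.

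| PDQ-39 evaluable | Fixed 2.5% | Holm | Gain (points) |
|---|---|---|---|
| 120 | 82.2% | 88.7% | 6.5 |
| 130 | 85.4% | 91.0% | 5.6 |
| 149 | 90.2% | 94.3% | 4.1 |
| 160 | 92.2% | 95.6% | 3.4 |
| 180 | 95.0% | 97.4% | 2.4 |
| 199 | 96.8% | 98.4% | 1.6 |

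More than 149 evaluable requires fewer than 25% to lack a week-18 PDQ-39. Membership of the full analysis set does not ensure this, because Section 9.7.1.2 admits a subject with either off time or PDQ-39 after dosing.

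If the PDQ-39 effect is 10, 20 or 30% smaller (an assumption), power at 149 goes from 82.6 to 89.0%, 72.1 to 80.8% and 59.2 to 69.8%. If the off-time effect is weak, the gain fades: at n = 149 and correlation 0.3 it is 3.8 points at a change of -0.78, 1.9 at -0.5, 0.5 at -0.3 and 0.1 at 0. The chance that at least one endpoint is significant is the same under both procedures.

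**4. When the conclusion would differ.** The critical mean change is t × 10.86/√n.
- n = 149: 10.86/12.21 = 0.890; 2.264 × 0.890 = 2.01 at 2.5%, and 1.976 × 0.890 = 1.76 at 5%.
- n = 199: 10.86/14.11 = 0.770; 2.259 × 0.770 = 1.74, and 1.972 × 0.770 = 1.52.

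Only an observed improvement between 1.76 and 2.01 points (149), or between 1.52 and 1.74 (199), would be read differently.

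**5. What Holm would cost.**
- Off time works, PDQ-39 null: the PDQ-39 false rejection rate rises from 2.5% to about 5.0%. In the direction of benefit that is 1.25% to 2.5%.
- PDQ-39 works, off time null: with independence the off-time rate is 0.025 + 0.025 × 0.902 = 4.75%; across correlations 0 to 0.5 it is about 4.5 to 4.8%.
- Both null: any rejection is the same under both procedures (4.8% simulated at correlation 0.3).

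**The case for a change.** The strongest argument for acting is that the missing rule matters most in a trial like this one. It is open-label and single-arm, so a rule chosen after pooled changes have been seen would carry little weight. On the plan's inputs there is about a 10% chance that off time succeeds and PDQ-39 does not; with a PDQ-39 effect 10 to 30% smaller, that becomes 17 to 41% (100 - 82.6 to 100 - 59.2). One sentence would settle the reading. And Holm's advantage over the fixed split holds by construction: its first step is the fixed 2.5% test.

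What stands is that the rule is absent from the text supplied and is best written down before lock. Section 9.7.1 already provides the place and the deadline for that. Writing it changes no test, no level and no sample size. Meanwhile each endpoint can be reported against its own 2.5% level, which suits a primary objective (Section 8.1) framed as evaluating change in both measures.

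The Holm argument does not carry over. It needs an either-endpoint claim and an overall 5%, and the protocol states neither. The co-primary label and its motor and non-motor rationale fit a both-must-succeed design at least as well, and in that design Holm is not needed. Section 9.7.1 also applies 2.5% to efficacy endpoints generally, so it covers 2 + 5 = 7 paired tests. A level shared by seven tests is weak evidence of a two-way split of 5%.

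**Conclusion.** No change to the plan follows. The unstated success rule is a gap that the SAP can fill before database lock, and the SAP may already do so. The fixed 2.5% tests are valid on either reading and deliver the stated 90% power with the protocol's own inputs.

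Replacing them with Holm is a fair trade-off that the sponsor may decline. It would gain 4.1 points of PDQ-39 power at 149 evaluable and 1.6 points at 199, and would alter the conclusion only within a band about 0.25 points wide (2.01 - 1.76) at 149. In exchange it would double the PDQ-39 false rejection rate, from 2.5% to about 5%, when only off time responds, and would relax a stated threshold in an uncontrolled, unblinded study.

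These gains rest on an either-endpoint claim, an overall two-sided 5%, and the planned off-time effect. If both endpoints must succeed, keeping 2.5% each is simply the stricter choice.
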